2.1. Study design

The PEOPLE study is a cluster randomized trial. There will be four door-to-door surveys of which the first one will allow us to calculate a baseline leprosy prevalence

per island. On the Comoros villages have been randomized after having been grouped by island into 'Blocks' of four in decreasing order of incidence over the period 2013-2017. Within each block villages were randomly and mutually exclusively allocated to the four study arms. For the study district in Madagascar reliable incidence estimates were not available. For that reason randomization for Madagascar is foreseen only for the end of the first study year, once the first screening round has been completed.

There will be four study arms to which villages on Madagascar and the Comoros islands Anjouan and Mohéli will be randomly allocated. These villages have been preselected based on reported leprosy incidence over the period 2013-2017. In all four study arms, annual door-to-door surveys will be conducted covering entire villages. All permanent residents will be invited for screening for leprosy. Leprosy patients (further referred to as 'index patients') detected will be offered free treatment according to the international and country guidelines. Depending on the study arm, contacts of leprosy patients will be offered PEP. In arm 1 no PEP will be provided, which is the current routine care on Madagascar and the Comoros. In arms 2, 3 and 4 a single dose of 20 mg per kg bodyweight of Rifampicin (hereafter called 'SDDR-PEP') will be offered to all eligible participants who have not received Rifampicin in the preceding 2-year period. In arm 2 only household contacts of an index patient will be provided with SDDR-PEP, which target group is considered the standard approach when PEP is provided for leprosy. In arms 3 and 4 SDDR-PEP will also be provided to neighbourhood contacts living within a radius of 100 meter of an index patient. In arm 3 all such contacts (including household contacts) will be provided SDDR-PEP, in arm 4 SDDR-PEP will be provided to all household contacts and to all those within the 100-meter perimeter testing positive to a serological screening test. If in arms 3 or 4 more than 50% (arm 3) or 75% (arm 4) of the population live within 100 meters of an index case, the entire village will in principle be eligible for PEP.

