2.2. Study objectives

Primary objective:

To compare effectiveness in curbing transmission of leprosy of three different approaches of post exposure prophylaxis

Secondary objectives:

1. To assess cost and feasibility of SDDR-PEP under program conditions
2. To identify patterns of clustering in transmission of leprosy, allowing better targeting of control measures
3. To monitor rifampicin resistance among leprosy patients
4. To estimate incidence and prevalence of smear positive pulmonary tuberculosis in the study villages

3. Deviations from protocol

In the protocol one of the secondary objectives was to estimate incidence and prevalence of smear positive pulmonary tuberculosis (see section above). The criterion to collect sputum was reported cough of 2 weeks duration or more. On a total population screened of just over 102,000 during the first year, only 115 (0.11%) reported such

cough. Either the question is not properly understood or cough is not a good screening criterion in the context of this study population. It was therefore decided to drop this secondary objective.

4. Description of study population

The study population will be described overall, and in each island (Anjouan, Mohéli, Madagascar) separately.

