Mixed effects Poisson model (same model as for the main analysis) with study arm (only when comparing 2019 to 2020 data) and distance to nearest index case as fixed covariates will be used to test for an association between distance to index case and leprosy incidence rate. We will compare six distance categories: same household, neighbors at < 25 meters and neighborhood contacts at 25-<50 meters, at 50 - < 75 meters, at 75 - < 100 meters and at 100 meters or beyond. Two models will be fitted. The first model will use leprosy diagnosis at the time of the survey in 2019 (either a new diagnosis or a patient still on treatment) as outcome and distance to nearest index case from 2019 as independent variable, the second model will use incident leprosy cases in 2020 as outcome and distance to nearest index case from 2019 as independent variable. In addition we will use Kulldorff's spatial scan statistic to fit a purely spatial Poisson model to identify clusters of high leprosy prevalence.

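### The section 8.2 model of 2020 cases by distance adjusts for study arm only as a main effect, so its distance ratios mix the underlying gradient with the PEP allocation; a supplementary model would help (minor)

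*SAP*

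**What the plan says.** SAP section 8.2 plans two distance models with six categories, from same household to 100 m or beyond. The first relates leprosy found in 2019 to distance from a 2019 index case. The second relates 2020 incident cases to that same distance. The fixed part is described as "with study arm (only when comparing 2019 to 2020 data) and distance to nearest index case as fixed covariates", so arm enters only the second model. The aim is modest: the model "will be used to test for an association between distance to index case and leprosy incidence rate". No interaction and no PEP term is named. The main model in section 7, which section 8.2 reuses, has arm as its only explanatory variable, plus random effects for island, block and village.

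Section 2.1 allocates PEP as follows. Arm 1 has none. "In arm 2 only household contacts of an index patient will be provided with SDDR-PEP". "In arm 3 all such contacts (including household contacts) will be provided SDDR-PEP", where the contacts meant include neighbours up to 100 m away. For the last arm, "in arm 4 SDDR-PEP will be provided to all household contacts and to all those within the 100-meter perimeter testing positive" on serology. Above 50% (arm 3) or 75% (arm 4) of residents within 100 m of an index case, "the entire village will in principle be eligible for PEP".

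Madagascar differs in timing: "randomization for Madagascar is foreseen only for the end of the first study year". Section 5.1 brings its first-survey data into this objective, while section 7 counts cases only after the enrolment survey. It is therefore unclear whether its first-to-second-survey interval, which has no trial PEP, enters the second model.

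**The concern.** In arms 2 to 4 the exposure under study, distance, also decides who is offered the intervention. One coefficient per arm, or one effect per village, moves all six distance categories up or down together. If PEP works, part of its effect therefore ends up in the distance ratios.

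Objective 2 is there to help aim control measures. Someone using the 2020 ratios for that purpose would want to know the risk near an untreated index case. What the planned model gives is the risk near an index case whose contacts were often offered PEP. The 2019 model is not affected. A reader who sets the two gradients side by side could take a flatter 2020 gradient as lower natural risk close to index cases, when PEP alone could have produced it.

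**Working it through.** The SAP gives no figure on this point, so there is none to reproduce.

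**Step 1. Who is offered PEP (section 2.1).**

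| Arm | Household | Other, under 100 m | 100 m or beyond |
|---|---|---|---|
| 1 | no | no | no |
| 2 | yes | no | no |
| 3 | yes | yes | only with whole-village PEP |
| 4 | yes | seropositives; all with whole-village PEP | only with whole-village PEP |

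Whole-village PEP is read here as everyone eligible.

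**Step 2. Formula.** Let e be the protection in recipients (1 minus the rate ratio), equal at all distances; u the uptake; w the share of arm 3 and 4 villages under whole-village PEP; and m the share of person-time from Madagascar's interval without PEP. With equal arms and the same distance mix in each, a main-effects Poisson model returns the ratio of rates averaged over arms. The household ratio against 100 m or beyond is multiplied by

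F = [1 − 0.75·u·e·(1 − m)] / [1 − 0.5·w·u·e·(1 − m)].

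The 0.75 is the three of four arms that offer household PEP. The 0.5 is the two of four that can reach beyond 100 m. With u = 1 and w = m = 0 this is 1 − 0.75e, that is 0.81, 0.625 and 0.55 at e = 25%, 50% and 60%.

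**Step 3. Illustration.** None of these inputs is in the SAP. Assume ratios without PEP of 4.0, 2.5, 2.0, 1.5 and 1.2 for the five nearer categories; 30% seropositive; and recipient rate ratios of 0.75, 0.5 and 0.4. Section 7 gives eight, four and four to six blocks, with four villages per block (section 2.1). Madagascar therefore has 16 of 64 (25%) to 24 of 72 (33%) villages, used here as m. Fitted household ratios, where 4.0 would mean no distortion:

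| Scenario | m = 0 | m = 25% | m = 33% |
|---|---|---|---|
| (i) u = 1, w = 0 | 3.25 / 2.50 / 2.20 | 3.44 / 2.88 / 2.65 | 3.50 / 3.00 / 2.80 |
| (ii) u = 0.7, w = 0.5 | 3.63 / 3.23 / 3.06 | 3.73 / 3.44 / 3.32 | 3.76 / 3.50 / 3.40 |
| (iii) u = 0.5, w = 1 | 3.87 / 3.71 / 3.65 | 3.90 / 3.79 / 3.75 | 3.91 / 3.82 / 3.78 |

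Example, (ii) at e = 0.5 and m = 0: u·e = 0.35, so F = (1 − 0.2625)/(1 − 0.0875) = 0.808, and 4.0 × 0.808 = 3.23. The shortfall runs from 3% to 45% without Madagascar's interval and from 2% to 34% with it. It is zero if PEP has no effect.

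The other categories under 100 m move less. At 75 to 100 m, a true 1.2 becomes 1.10 / 1.00 / 0.97 in (i), 1.16 / 1.13 / 1.11 in (ii), and stays 1.20 in (iii). Giving whole-village villages their own intercept leaves the household ratios in (ii) unchanged, so village effects do not absorb the problem.

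**Step 4. When the direction changes.** Let protection be e_h in households and e_o elsewhere, with m = 0. Then F = (1 − 0.75·u·e_h)/(1 − 0.5·w·u·e_o), which exceeds 1 when e_h < (2/3)·w·e_o. In (iii) with e_h = 0.25 and e_o = 0.5, F = 0.90625/0.875 = 1.036 and the ratio is 4.14. With e_o = 0.6 it is 4.27.

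**Step 5. A model with eligibility terms.** Add two terms: eligible outright, and eligible only if seropositive. With one PEP effect this returns 4.0, by construction of the data. Assume 200 cases, about 2.0 per 1,000 of the population in section 3 ("On a total population screened of just over 102,000 during the first year"). The standard error of the log household ratio is then 1.13 to 1.40 times that of the planned model without Madagascar's interval, and 1.01 to 1.24 times with it. Root mean square error of the log ratio without that interval, planned v added terms:

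- (i) 0.307 v 0.317, 0.529 v 0.322, 0.649 v 0.326
- (ii) 0.241 v 0.253, 0.312 v 0.259, 0.353 v 0.262
- (iii) 0.221 v 0.247, 0.233 v 0.249, 0.240 v 0.250

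The planned model has the smaller error in 5 of 9 cells. If households are protected less (rate ratio 0.75 against 0.5 or 0.4 elsewhere), the added-term model gives 4.70 to 5.04 in (i) against 3.25 planned, and 4.62 to 4.92 in (ii) against 3.81 to 3.88 planned. Arm 1 alone needs no such assumption but would hold about 8 household cases (standard error of the log ratio about 0.40).

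**The case against.** The strongest reply is that section 8.2 sets out only to test an association, and the planned ratio answers that as an average over the trial's arms. This stands. A reader might infer that the model is invalid, but the SAP never promises a gradient without PEP.

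A reader might also infer that the SAP plans to compare the 2019 and 2020 gradients. It fits both models but states no such comparison, and the outcomes differ anyway: the 2019 one includes patients still on treatment. Nor does targeting rest on this model alone. Section 8.2 gives the 100 m question to the network overlay and adds fingerprinting, the space-time K-function and a spatial scan. The primary analysis is untouched.

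The sizes are all assumed, and two assumptions are open to challenge:

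- Non-recipients may be protected indirectly. If all non-recipients in arms 2 to 4 have a rate ratio of 0.7 and recipients 0.5, the household ratio is 4 × 0.625/0.775 = 3.23 in (i) and 4 × 0.67/0.74 = 3.62 in (ii). The shortfall shrinks but remains.
- The precision figures assume 40% of residents within 100 m everywhere, which would not trigger whole-village PEP. With dense villages (82%) triggering it and sparse ones not, and separate intercepts, the ratio in (ii) at rate ratio 0.5 stays 3.23. The gain from the added terms narrows to 0.324 v 0.302, and at rate ratio 0.75 the planned model does better, 0.258 v 0.299.

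Finally, the eligibility-adjusted model often has the larger error and can mislead. This also stands, and it rules out making that model the sole basis for statements about targeting.

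**Conclusion.** The point holds as a minor improvement to one secondary model. With arm as a main effect only, and PEP offered by arm and distance together, the second model cannot separate a PEP effect from the distance gradient. Its ratios are a valid average association under the trial's PEP allocation. If PEP protects about equally at all distances, the household ratio lies below its value without PEP: by the factor 1 − 0.75e with equal arms, full uptake, no whole-village PEP and no Madagascar interval, and by less when those conditions are relaxed as above.

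It would be too strong to say that the gradient is understated by a known amount, or always understated. The SAP gives no PEP effect, uptake, gradient or case count. The direction can reverse when households are protected clearly less than others and whole-village PEP is universal.

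**What to change.** In section 8.2, keep the planned model as the test of association and state that its ratios are those observed under the trial's PEP allocation.

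Pre-specify one supplementary model that adds terms for PEP eligibility as actually in force:

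- eligible outright;
- eligible only if seropositive;
- whole-village PEP coded as eligible at every distance;
- Madagascar's first-to-second-survey interval, if included, coded as no PEP. The SAP should say whether it is included.

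Show the arm 1 gradient descriptively. Report all three together as sensitivity results, with none of the added ones as the sole basis for targeting. Add a sentence that a flatter 2020 gradient from the planned model is not to be read as lower natural risk near index cases.

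The cost is SAP wording and one extra fit. The supplementary household estimate is less precise and relies on a single PEP effect across arms and distances. The arm 1 gradient avoids that assumption but rests on few household cases.

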8.1. To assess cost and feasibility of SDDR-PEP under program conditions

Costs will be calculated per person screened, per person treated with SDDR-PEP and per leprosy case averted.

8.2. To identify patterns of clustering in transmission of leprosy, allowing better targeting of control measures

Results of DNA finger printing will be used to assess the degree of clustering at household and at village level. We will calculate proportions of patients belonging to a same cluster by household and by village. The space-time K-function will be used to assess clustering in time and space, to be triangulated with results of DNA finger printing. For this purpose, we will use results of all leprosy patients identified, including those found at baseline.

To establish the transmission networks in the Comoros islands and in the study area in Madagascar, we will overlay the molecular network with the spatial- and social networks. This will determine whether the 100m high risk zones around each index patient, applied in this study, capture most transmission events, or whether additional risk factors, beyond spatial, need to be taken into account in future PEP administration efforts in the study areas and elsewhere. Phylogenetic clustering of the *M. leprae* isolates allows us to identify risk factors for leprosy due to recent transmission. The findings of the spatial and social network analysis can be mapped onto a phylogenetic tree and molecular clusters based on the VNTRs, which can reveal risk factors for transmission of leprosy.

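### The distance models in SAP Section 8.2 pool everyone farther than 100 m from an index case, so they cannot show whether, or how far, excess risk extends past the intervention radius

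*SAP*

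**What the plan says.** SAP Section 8.2 plans two mixed effects Poisson models with distance to the nearest 2019 index case as a covariate. One takes leprosy present at the 2019 survey as outcome, the other incident cases in 2020. The distance scale is categorical: "We will compare six distance categories: same household, neighbors at < 25 meters and neighborhood contacts at 25-<50 meters", then 50 to under 75 m, and finally "at 75 - < 100 meters and at 100 meters or beyond". No reference category, continuous distance term or cut point above 100 m is given. The stated purpose is that the model "will be used to test for an association between distance to index case and leprosy incidence rate".

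The 100 m limit is also the intervention radius. Under SAP Section 2.1, arms 3 and 4 extend prophylaxis to "neighbourhood contacts living within a radius of 100 meter of an index patient" (in arm 4, outside the household, only to those with a positive serological test).

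Earlier in Section 8.2 the SAP raises the adequacy of that radius and ties it to a different analysis. It says "we will overlay the molecular network with the spatial- and social networks", and then: "This will determine whether the 100m high risk zones around each index patient, applied in this study, capture most transmission events". Two further spatial analyses are planned in the same section. For the first, "The space-time K-function will be used to assess clustering in time and space, to be triangulated with results of DNA finger printing". The second is a "spatial scan statistic to fit a purely spatial Poisson model to identify clusters of high leprosy prevalence". Neither is stated to be limited to 100 m.

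**The concern.** The categories give fine resolution inside the zone where prophylaxis is offered and none outside it. Outside is where a radius that is too short would show, as risk still raised just past 100 m and falling farther out. A resident at 110 m and one at 800 m get the same covariate value.

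Two things are at stake. First, the models lose the information on where excess risk ends, which bears on the section's declared aim of better targeting. Second, if the outer group serves as comparator, any excess just outside 100 m is mixed into the comparison rate and the inner rate ratios shrink.

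**Working it through.** **Count of categories.** The SAP says six, and the list gives six: same household, <25, 25-<50, 50-<75, 75-<100, and ≥100 m. Five are inside 100 m and one is outside. Contrasts between distances beyond 100 m: zero. The only contrasts across the boundary set an inner category against the whole outer group.

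**Inputs not in the SAP.** It gives no rates and no person-time by distance. All values below are assumptions chosen to show the mechanism. Let f be the share of ≥100 m person-time that lies at 100-<200 m, r the rate there, and b the rate at ≥200 m. Then

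pooled outer rate = f × r + (1 − f) × b.

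**Step 1: different patterns give the same category rate.** Take f = 0.4.
- Excess just outside: r = 1.5, b = 1.0 gives 0.4 × 1.5 + 0.6 × 1.0 = 1.2.
- Flat beyond 100 m: r = 1.2, b = 1.2 gives 0.4 × 1.2 + 0.6 × 1.2 = 1.2.

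The true ratio of 100-<200 m to ≥200 m is 1.5 in one case and 1.0 in the other, yet the planned categories see 1.2 in both. This holds whichever category is the reference.

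**Step 2: effect on inner rate ratios if the outer group is the reference.** Set b = 1. The pooled rate is 1 + f × (r − 1), and the observed ratio is the true ratio divided by it.

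True ratio 2.0 for an inner category:
- f = 0.3, r = 1.2: pooled 1.06, observed 2.0/1.06 = 1.89
- f = 0.4, r = 1.3: pooled 1.12, observed 2.0/1.12 = 1.79
- f = 0.5, r = 1.5: pooled 1.25, observed 2.0/1.25 = 1.60

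True ratio 1.5 at 75-<100 m, with the same 1.5 continuing to 200 m:
- f = 0.2: 1.5/1.1 = 1.36
- f = 0.4: 1.5/1.2 = 1.25
- f = 0.6: 1.5/1.3 = 1.15
- f = 0.8: 1.5/1.4 = 1.07

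With no excess beyond 100 m (r = 1), the pooled rate is 1 and nothing is attenuated. Contrasts among the inner categories do not involve the outer group and are unaffected in every case.

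**Step 3: what the other Section 8.2 analyses are described as giving.**
- Network overlay: links among patients, resting on molecular data. It is the analysis assigned to the 100 m question.
- Space-time K-function: clustering of cases in time and space.
- Spatial scan statistic: location of high-prevalence clusters.

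None is described as estimating the rate among residents at a given distance from an index case. The Poisson models do that, and they stop resolving distance at 100 m.

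**The case against.** The strongest reply is that the models are being asked to do another analysis's job. Their stated purpose is to test for an association with distance, and six categories can do that. The SAP gives the 100 m question to the network overlay, and the K-function and scan statistic can look past 100 m. This stands. A reader might infer that the secondary objective goes unanswered. The documents do not support that: the objective as listed in SAP Section 2.2 concerns clustering patterns and sets no distance limit.

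The question put to the overlay can also be read as the share of transmission inside against outside 100 m, for which one cut at 100 m is enough. That is fair for the share. It does not tell the reader how far raised risk reaches, or whether a different radius would add much, which is what targeting would use.

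A reader might also infer that the categories make 100 m look wide enough whatever the truth. That does not follow. The model can compare 75-<100 m with the outer group, and a higher rate there would suggest that risk has not levelled off by the boundary. Excess risk outside would draw the inner ratios toward 1, which weakens the apparent distinctness of the zone and does not confirm it.

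Finally, the attenuation requires the outer group to be the reference, which the SAP does not say. Some villages may also have few residents beyond 100 m: Section 2.1 provides for those where more than 50% (arm 3) or 75% (arm 4) live within it. Both points stand. The second limits how finely the outer group can be split.

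**Conclusion.** The point holds as a limited weakness of two secondary models. As specified, they cannot distinguish risk that ends at 100 m from risk that continues past it. That rests only on the category list and needs no assumption.

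The attenuation of inner rate ratios (2.0 read as 1.89 to 1.60 in the illustration) is conditional on the outer group being the reference and on assumed rates and person-time shares. It shows direction and mechanism and is not an estimate for this trial. There is no internal contradiction in the SAP and no effect on the primary analysis. The change is a minor improvement, worth making because it is cheap.

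**What to change.** In both distance models, keep the five inner categories and split the outer group with at least one further cut point, for example 100-<200 m and 200 m or beyond, provided each band has adequate person-time. Alternatively, add a continuous distance term. Name the farthest band as the reference. Report the rate ratio for the band just outside 100 m with its confidence interval, as supporting evidence alongside the network overlay. The 200 m value is only an example. The cut should be fixed from the distribution of person-time by distance, without reference to outcomes.

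Cost: one or two extra parameters in secondary models. No new data should be needed, since placing people in 25 m bands already requires their distance to the nearest index case. The downside is wider intervals, which could be marked if few residents live far from an index case.
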